#### 4.4.2.3 UC-PRO

The UC-PRO questionnaire is collected in the e-diary and completed by patients for at least 9–12 consecutive days prior to a study visit as per the Schedule of Assessments in the protocol. The UC-PRO is being reported in three domains; two domains are key endpoints and reported as UC-PRO Signs and Symptoms. This data was not collected in the GA29103 study.

#### **4.4.2.3.1 Functional and Bowel Domain**

Two domain scores computed for the UC-PRO Signs and Symptoms:

- Functional Symptoms
- Bowel Movement Signs and Symptoms

There is no single total score. The questions contributing to each domain are shown in [Appendix 6](#). The functional domain score ranges from 0–12, the bowel domain score ranges from 0–27, with a higher score indicating a worse disease state. The responder definition cutoffs for the Functional and Bowel domains will be pre-specified in the Data Analysis Plan (DAP).

The daily scores contributing to the UC-PRO/SS calculation for a visit will be selected as: most recent 7 daily scores available prior to but not including a visit. (Note: a minimum of 4 days is required.)

For each item in the questionnaire, a score will be calculated for a visit by taking the average of the most recent 7 daily scores available. The domain score for a visit will then be determined, taken as the sum of the (averaged) items for each question.

The endpoint using the UC-PRO/SS is the change from baseline at Week X in UC-PRO/SS Domain as assessed by UC-PRO/SS measure.

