The symptoms of UC must be recorded throughout the study, including the screening period. The e-diary entries will be reviewed by site personnel during screening (prior to dosing, if applicable) and during study visits, including the early withdrawal from treatment visit and any unscheduled visits due to disease exacerbation. Because the colonoscopy/flexible sigmoidoscopy and bowel cleansing preparations can interfere with the assessment of patient-reported symptoms, e-diary entries used to calculate the complete MCS should not correspond to days of bowel preparation or endoscopy or the day following the endoscopy. Further details and examples of stool frequency and rectal bleeding subscore derivation are provided in [Appendix 4](#).

Colonoscopy/Flexible Sigmoidoscopy with Colonic Biopsies

Patients are to prepare their bowel prior to the colonoscopy/flexible sigmoidoscopy procedures. Medications used for bowel preparation should be recorded on concomitant medications pages of eCRF.

Stool samples for analysis of fecal calprotectin and other exploratory biomarkers (such as analyses of the microbiota and bacterial cultures) are to be collected prior to bowel preparation (polyethylene glycol [PEG]–based preparation or enema).

Full colonoscopy within a year of screening is required to ensure against enrollment of patients with colonic carcinoma and dysplasia. If full colonoscopy has not been performed within the year before screening, it should be conducted in place of the flexible sigmoidoscopy at screening. For patients not requiring a colonoscopy, a flexible sigmoidoscopy will be performed on all patients for inclusion in the study. Endoscopy will be performed during screening 4–16 days prior to Day 1.

Endoscopy will be also performed at Weeks 10 and 62 and/or at withdrawal from study (early withdrawal from treatment visit, see [Appendix 1](#)).

Central reading of endoscopies will be performed throughout this study, and a detailed charter will address the standardization of endoscopic procedures, video recordings, and

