4.5.2 Timing of Study Assessments

4.5.2.1 Screening and Pretreatment Assessments

Written informed consent for participation in the study must be obtained before performing any study-specific screening tests or evaluations. Informed Consent Forms for enrolled patients and for patients who are not subsequently enrolled will be maintained at the study site.

Etrolizumab—F. Hoffmann-La Roche Ltd
77/Protocol GA29102, Version 7

All screening tests and evaluations will be performed within 35 days prior to Day 1 except for flexible sigmoidoscopy/colonoscopy, which should be performed 4–16 days prior to Day 1 (see [Figure 4](#)). The screening period will not exceed 35 calendar days.

Laboratory samples should be collected from the patient early in the screening period to allow time for the laboratory results to be available for review by the site for eligibility (see Section [4.5.1.5](#)). The ECG and chest X-ray can be obtained any time before Day 1 (see Section [4.5.1.6](#) and Section [4.5.1.7](#) for additional details on the chest X-ray and ECG). Colon biopsy specimen collection is detailed in Section [4.5.1.4](#).

[figure not shown]
A blood sample to test for antibodies to JCV will be taken and stored for possible later assessment of how widespread the JCV infection is in the study population. Sample testing for the presence of JCV antibodies is not helpful in predicting risk for PML or for evaluating neurologic symptoms. The sample may be tested if there is a strong belief that this information will be helpful in managing a patient's condition.

The screening endoscopy for MCS should be performed 4–16 days prior to Day 1 (i.e., Day –16 to Day –4). The endoscopy score from the worst affected segment up to the splenic flexure (rectum, sigmoid, and descending colon) is to be used for the MCS calculation (see Section [4.5.1.4](#)).

The symptoms of UC must be recorded during the screening period. The e-diary entries will be reviewed by site personnel during screening. Because the colonoscopy/flexible sigmoidoscopy and bowel cleansing preparations can interfere with the assessment of patient-reported symptoms, e-diary entries used to calculate the complete MCS should not correspond to days of bowel preparation or endoscopy or the day following the endoscopy. Further details and examples of stool frequency and rectal bleeding subscore derivation are provided in [Appendix 4](#).

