4.5.2.2 Assessments during Treatment

All assessments will be performed on the day of the specified visit, except where a time window is specified. Assessments scheduled on the day of study drug administration should be performed prior to dosing, unless otherwise noted. When study drug administration in the home is required on the same day as a clinic visit, drug is to be administered at home AFTER the clinic visit.

For induction (Week 10) and maintenance (Week 62) visits that are associated with an MCS requiring endoscopy, every effort should be made to schedule the endoscopy on the same day as the clinic visit. If this is not possible, endoscopy should be performed as close to the clinic visit as possible, with a maximal window of 3 days prior to and 5 days after the visit. The endoscopy score should be considered when determining the PGA (as applicable), a component of the MCS (see [Appendix 4](#)).

On a number of occasions during the Maintenance Phase (see [Appendix 1](#) and [Figure 3](#)), patients will be contacted by telephone for the purpose of study assessment, rather than making a clinic visit. During these telephone visits, data will be collected as for a clinic visit with the exception of blood sample and in clinic PRO assessments (see [Appendix 1](#), Schedule of Assessments). All adverse events and concomitant medications will be recorded and the patient questioned regarding a potential clinical relapse. An unscheduled visit is to be conducted as required (see Section [4.5.2.5](#)).

All patients will receive hands-on training in use of the e-diary and tablet. Patients will also be instructed to contact the site promptly if they have any questions about the use of the e-diary during screening or at any time during the study.

See [Appendix 1](#) for the schedule of assessments performed during the treatment period.

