Appendix 1 Schedule of Activities (cont.)

- ^r A blood sample to test for antibodies to JCV will be taken and stored for possible later assessment of how widespread the JCV infection is in the study population. Sample testing for the presence of JCV antibodies is not helpful in predicting risk for PML or for evaluating neurologic symptoms. The sample may be tested if there is a strong belief that this information will be helpful in managing a patient's condition.
- ^s Endoscopy + rectal bleeding assessment + stool frequency assessment + Physician's Global Assessment. Patients who have not undergone full colonoscopy with documented results within 1 year prior to screening should undergo colonoscopy in lieu of sigmoidoscopy at the screening visit to allow for screening for cancer/dysplasia (yes/no).
- ^t During screening, patients must be trained on the use of the e-diary. Patients are to complete the e-diary on a daily basis for the stool frequency and rectal bleeding score (for MCS/pMCS), starting from the first screening visit, and for at least 9–12 consecutive days around the time of each scheduled visit for the UC-PRO/SS.
- ^u Screening endoscopy (for the MCS) should be performed 4–16 days prior to Day 1 (i.e., Day –16 to Day –4). For baseline measurements, the Physician's Global Assessment will be obtained only once, on Day 1 (prior to enrollment), and the Physician's Global Assessment score will be used to calculate both the baseline (screening) MCS and the baseline (Day 1) pMCS.
- ^v Rectal bleeding assessment + stool frequency assessment + Physician's Global Assessment.
- ^w For culture and sensitivity testing; ova, parasites, and Clostridium difficile toxin testing.
- ^x Sample analyses may include, but are not limited to, analyses of fecal calprotectin and other exploratory PD biomarkers (such as analyses of the microbiota and bacterial cultures).
- ^y IF REQUIRED: Only if there is suspicion for clinically significant CMV colitis, one biopsy sample should be obtained from the base of the ulcer to evaluate for histological presence of CMV. Analysis should be performed locally if possible, or can be sent to a central laboratory if necessary. Result must be negative for CMV prior to dosing on Day 1.
- ^z IF REQUIRED: If patient does not have previously documented histopathologic confirmation of UC as defined in the inclusion criteria, one biopsy sample can be obtained from the base of the ulcer read locally for histopathologic confirmation of UC.

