Appendix 4 Mayo Clinic Score Measurement (cont.)

DATA COLLECTION REQUIREMENTS

Data will be collected on e-diary and other electronic media; during conversion to these media the format of the questions may change.

- A CRITICAL DATA POINT TAKEN AT BASELINE IS THE PATIENT'S NORMAL NUMBER OF STOOLS. This is defined as the number of stool passed when a patient is in remission/ not in flare. This is to be taken from the most recent available data in the patient's medical notes or taken during patient interview at screening. This value will remain stable throughout the study.
- Normal number of stools is to be rounded up (e.g., normal number of stools=1–2 would be rounded to 2)
- The NORMAL number of stools is to be recorded on the e-diary and made visible to the patient to assist with their scoring relative to this number

NOTE: Data recorded during bowel preparation procedures and day of endoscopy is to be ignored (bowel preparation and endoscopy procedure days are to be loaded onto the e-diary by the patient and excluded from the MCS calculation)

1. Stool frequency

- Stool frequency is to be recorded daily from start of screening to the end of the study in the e-diary
- The stool frequency is to be compared with the patient's normal stool frequency and entered as a score between 0 and 3 (see 1 above) (e.g., a patient normally has 1 stool per day and today has 4 stools. Therefore the patient has 3 stools more than "normal," which yields a value of 2 for that day.)
- The stool frequency will be defined as the passage of solid or liquid fecal material. Episodes of incontinence count. A non-productive trip to the bathroom or the simple passage of gas DOES NOT COUNT as stool.

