**Table 2 Steps for Calculating SF/RB Subscore**

Timepoint	Scenarios to calculate SF/RB Subscore
Baseline	
Scenario 1 Bowel preparation date (prior to an endoscopy) is assigned as the ‘anchor’ date. Three days daily diary data collected from patient’s e-diary between Day -22 and the day prior to the anchor date will be selected to calculate SF/RB scores. Daily dairy days selected closest to the anchor date will be selected first

	
Scenario 2 Bowel preparation date (prior to an endoscopy) is assigned as the ‘anchor’ date. If fewer than three days of daily diary data are available between Day –22 through to the day prior to the anchor date, then additional daily diary data collected post endoscopy starting with the score recorded 2 days after the endoscopy but prior to the randomization/enrollment will be selected to calculate SF/RB scores. Examples of this scenario are illustrated (see Appendix 3).

	
Scenario 3 Randomization/Enrollment Date is assigned as the ‘anchor’ date, if endoscopy did not occur between Day -21 and day prior to randomization/enrollment date. Three days worth of diary data prior to the ‘anchor’ date will be selected to calculate SF/RB scores. Daily dairy days selected closest to the anchor date will be selected first

Post Baseline	
Scenario 1 Bowel preparation date (prior to an endoscopy) occurring within 7 days prior to the visit date is assigned as the ‘anchor’ date. Three daily diary days collected within the 7 days prior to post baseline visit date will be selected, to calculate SF/RB scores. Daily dairy days selected closest to the anchor date will be selected first. Visit date is the day the PGA assessment is collected.
 
Scenario 2 Bowel preparation date (prior to an endoscopy) is assigned as the ‘anchor’ date. Three daily diary days collected within the 7 days prior to post baseline visit date will be selected, to calculate SF/RB scores. Daily dairy days selected closest to the anchor date will be selected first.
 
If further days are required, data collected +2 days after endoscopy within the 7 days prior to visit date will be used. Visit date is the day the PGA assessment is collected.

	
Scenario 3 Visit date is assigned as the ‘anchor’ date. Three daily diary days collected within the 7 days prior to post baseline visit date will be selected, to calculate SF/RB scores. Daily dairy days selected closest to the anchor date will be selected first.

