## Appendix 6 Ulcerative Colitis Patient Reported Outcomes Signs and Symptoms (contd.)

UC-PRO/SS Domain	Question	Response to Question
Bowel Movement Signs and Symptoms	In the past 24 hours, how many bowel movements did you have?	0=0, 1=1-2, 2=3-4, 3=5-6, 4=7-9, 5=10-12, 6=13-17, 7=18 or more
	In the past 24 hours, how often were your bowel movements mostly or completely liquid?	0=Never 1=Rarely 2=Sometimes 3=Often 4=Always
	In the past 24 hours, did you have blood in your bowel movements?	0=No 1=Rarely 2=Sometimes 3=Often 4=Always
	In the past 24 hours, did you have mucus (white material) in your bowel movements?	0=No 1=Rarely 2=Sometimes 3=Often 4=Always
	In the past 24 hours, did stool, blood, or liquid leak out before you reached a toilet?	0=No 1=Rarely 2=Sometimes 3=Often 4=Always
	In the past 24 hours, did you feel the need to have a bowel movement right away?	0=No 1=Mild 2=Moderate 3=Severe 4=Very Severe

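### UC-PRO/SS visit scores keep the bowel-preparation, endoscopy and day-after entries that the plan bars from the Mayo score, and the SAP 4.8 fallback can let the preparation day into the Mayo score as well

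*SAP*

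**What the plan says.** **UC-PRO/SS.** Project SAP 4.4.2.3.1 averages each item over the "most recent 7 daily scores available prior to but not including a visit" (at least 4 days needed) and sums the item means. Only the visit day is left out. Neither Protocol 4.5.1.8 nor project SAP 4.4.2.3 or 4.8 adds an exclusion. The diary is kept for at least 9–12 "consecutive days around the time of each scheduled visit for the UC-PRO/SS" (Protocol Appendix 1); project SAP 4.4.2.3 places those days before the visit.

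**Mayo score (MCS).** Protocol 4.5.1.4 requires that "e-diary entries used to calculate the complete MCS should not correspond to days of bowel preparation or endoscopy or the day following the endoscopy". The reason, repeated in 4.5.2.1, is that endoscopy and "bowel cleansing preparations can interfere with the assessment of patient-reported symptoms". Protocol Appendix 4 adds that "bowel preparation and endoscopy procedure days are to be loaded onto the e-diary by the patient and excluded from the MCS calculation". Project SAP Table 2 takes diary days before the preparation date (the anchor, itself not used). If more are needed after endoscopy, "data collected +2 days after endoscopy within the 7 days prior to visit date will be used".

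**Timing.** Week 10 and Week 62 endoscopies should fall on the visit day, otherwise "with a maximal window of 3 days prior to and 5 days after the visit" (Protocol 4.5.2.2). Screening endoscopy is on Day -16 to Day -4.

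**Fallback.** When the preparation date is missing, project SAP 4.8 allows the endoscopy date to serve as the anchor.

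**The concern.** UC-PRO/SS is a daily patient report with 24-hour recall. Its bowel domain begins with "In the past 24 hours, how many bowel movements did you have" and goes on to liquid stools, leakage and urgency; the functional domain asks about gas, pain and bloating. Bowel preparation acts on these symptoms directly, and the protocol's reason for cleaning the MCS is stated for patient-reported symptoms in general. The SAP gives no reason for treating the two instruments differently.

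The project SAP calls the two domains key endpoints, and UC-PRO/SS appears in the legend of the study SAP's multiple-testing figure. After Week 10, the only scheduled endoscopy is at Week 62, so the disturbance falls on the endpoint visit. It can raise Week 62 means in both arms, add noise because the number of affected days differs between patients, and possibly shrink the difference. Responder cutoffs are also planned; a common shift that cancels in a difference of means does not cancel at a fixed threshold.

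The 4.8 fallback is a separate fault with the same cause, and it reaches the MCS used for the primary endpoint.

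**Working it through.** **1. The plan's own figures.** From the response codes in project SAP Appendix 6, the bowel maximum is 7 + 5×4 = 27 and the functional maximum is 3×4 = 12. Both match 4.4.2.3.1. The plan gives no SD, effect size or power for UC-PRO/SS.

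**2. Affected days at Week 62.** Let e be the endoscopy day relative to the visit. I count how many of e−1 (preparation), e and e+1 fall in days −7 to −1. One preparation day on the day before endoscopy is an assumption, but it matches the scenarios in Protocol Appendix 4 (endoscopy Day -16 with preparation Day -17; Day -4 with Day -5). Diaries are taken as complete.

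| e | Days in window | Affected (k) | k/7 |
|---|---|---|---|
| 0 (default) | preparation | 1 | 14.3% |
| −1 | preparation, endoscopy | 2 | 28.6% |
| −2 or −3 | all three | 3 | 42.9% |
| +1 to +5 | none | 0 | 0% |

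If preparation is an enema on the endoscopy day, the counts at 0, −1, −2 and −3 are 0, 1, 2 and 2.

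**3. Baseline.** The window is Day -7 to Day -1. Endoscopy on Day -8, -7, -6, -5 or -4 gives 1, 2, 3, 3 or 3 affected days; Day -16 to -9 gives none. So 5 of the 13 permitted days affect baseline, and change from baseline is not like for like.

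**4. Rise in the visit score.** Rise = k × s/7, where s is the excess per affected day (assumed; not in the documents). One illustration from the response codes: 1–2 to 10–12 movements (+4), liquid never to always (+4), urgency none to moderate (+2), so s = 10.

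- s = 10: 10/7 = 1.4, 20/7 = 2.9 and 30/7 = 4.3 points on the 0–27 scale for k = 1, 2 and 3.
- s = 3: 3/7 = 0.43 points for k = 1 and 9/7 = 1.29 for k = 3.

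**5. Shrinkage of the difference.** If the shift is purely additive and equal in both arms, 0% (with scores capped at 27, 1–2% for one day and 4–7% for three). If affected days carry no treatment signal, k/7, that is 14%, 29% or 43%.

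**6. Power, on assumed inputs.** Simulation with 105 per arm, 3,000 trials per case, SD 4 or 6, scores kept within 0–27, etrolizumab mean 8, and the difference set for 90% power with no affected days. The shift is 10 (SD 4, one draw per patient), applied either additively or as a replacement. The test is a two-sample z-test, a simplification of the planned MMRM.

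- One affected day in everyone: 0.88–0.90.
- 70% with one day and 10% each with 0, 2 and 3: 0.85–0.87.
- 0, 1, 2 and 3 days equally common: 0.79–0.86.

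**7. The 4.8 fallback.** With the endoscopy date as anchor, the anchor day is skipped and the nearest earlier day is taken first. That is the usual preparation day, which Protocol 4.5.1.4 bars.

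Take remitters with rectal bleeding 0, three daily stool scores of 0 or 1, and endoscopy and PGA subscores of 0 or 1. Of the 8 diary triples, 4 round to a stool subscore of 0, each allowing all 4 endoscopy/PGA pairs (16 patterns). The other 4 round to 1, each allowing the 3 pairs that keep the MCS at 2 or less (12 patterns). Total: 16 + 12 = 28.

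Now let the preparation day replace the oldest diary day, leaving two days with sum t.

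- Preparation day scores 2: the mean (t+2)/3 rounds to 1 for t = 0, 1 or 2. Patterns that had stool 0 with endoscopy and PGA both 1 reach MCS 3: 4 patterns lost.
- Preparation day scores 3: those 4 are lost, and t = 2 gives 5/3, which rounds to 2 and fails the subscore limit: 2 triples × 3 pairs = 6 more. Total lost: 10.

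These are counts of patterns, not expected frequencies.

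**The case against.** The exclusion is written for the MCS alone, so the text does not contradict itself. The MCS uses three days and the worst bleeding score, so one bad day can decide it; a seven-day mean dilutes one day to a seventh. Every effect input is assumed. Where affected days carry no signal, the spread shrinks along with the difference, so the 14–43% overstates the loss of power; a calculation that holds the SD fixed (79%, 64% and 46% for one, two and three days in every patient) does not fit that model. Same-day scheduling is the stated aim, and there the loss is close to nil. An entry made before preparation starts would be clean, so one affected day is an upper bound in that case. As for 4.8, a patient with no fallback could be non-evaluable and so a non-responder anyway.

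Much of this stands, and it limits the size: no false positives, little loss by default, and no estimate from trial data. It does not answer the main point. The protocol's reason covers patient-reported symptoms generally, and seven-day averaging lessens the disturbance without removing it. On 4.8, having a fallback is right; the fault is an anchor date that selects a day the protocol bars when a better one is available at no cost.

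**Conclusion.** The concern holds, in two parts.

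For UC-PRO/SS this is a cheap improvement that should be made. As written, up to three of the seven scored days at Week 62 are days the protocol treats as unreliable for patient-reported symptoms, and one is under the preferred schedule if preparation is on the day before. The effect is noise and possible shrinkage, not bias towards a positive result. It is negligible for power if nearly all endoscopies are on the visit day, and moderate (0.79–0.87 against 0.90, on assumed inputs) if timing varies.

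For the 4.8 fallback, the rule is wrong as written against Protocol 4.5.1.4 and, compared with an anchor one day earlier, can turn a remitter into a non-remitter on the primary endpoint. How often preparation dates are missing is unknown.

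The Data Analysis Plan and Protocol Appendix 9 were not available, so an exclusion stated there cannot be ruled out.

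**What to change.** In project SAP 4.4.2.3.1, drop the bowel-preparation day, the endoscopy day and the day after. Then average up to the 7 most recent remaining daily scores before the visit (minimum 4, as now), at baseline, Week 10 and Week 62. Keep the current rule as a sensitivity analysis. If the omission is deliberate, say so and give the reason.

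In project SAP 4.8, when the preparation date is missing, use the endoscopy date minus 1 day as the anchor. This assumes a single preparation day; longer preparation would need an earlier anchor, and with a same-day enema it costs only one clean day.

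The cost is two SAP sentences and some reprogramming, since patients already load these dates onto the e-diary. The price in data is earlier or fewer contributing days. If all 9–12 diary days precede the visit, 9−3 to 12−3 = 6–9 clean days remain with endoscopy 2 or 3 days before, 7–10 at one day before and 8–11 on the same day, all above the minimum of 4. Fewer remain if some diary days fall after the visit.
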